ABBREVIATIONS	7
1. BACKGROUND	8-9
2. RATIONALE	9-10
3. THEORETICAL FRAMEWORK	10-11
4. RESEARCH QUESTION/AIM(S)	11
5. STUDY DESIGN/METHODS	11-12
6. STUDY SETTING	13
7. SAMPLE AND RECRUITMENT	13-16
8. ETHICAL AND REGULATORY COMPLIANCE	17-22
9. DISSEMINATION POLICY	22-23
10. REFERENCES	24-26
11. APPENDICES	27-45

KEY STUDY CONTACTS	
Chief Investigator	[name] (Highly Specialised Physiotherapist, Trauma and Orthopaedics and Senior Research Associate)
	[contact]
Study Co-ordinator	[name]
Sponsor	City, St Georges University of London
Sponsor Contact	Name: [name]/ [name] Position: Research Governance and Facilitation officer Address: St George's Joint Research Enterprise Office [name] [contact] Email: [contact]
Funder(s)	Non-funded Research is being conducted as part of a dissertation for an MRes in Clinical Research at London City university
Key Protocol Contributors	[name] ([contact]) [name] [contact] [contact]
Committees	Not applicable

STUDY SUMMARY	
Study Title	Patients' Experience and Acceptability of Using a Virtual Reality
	Headset as an adjunct to rehabilitation following major trauma: A
	Interview Study
Internal ref. no. (or short title)	VR in Major Trauma Rehab: A qualitative Study
Study Design	Qualitative
Study Participants	Major Trauma patients from St George's hospital
Planned Size of Sample (if applicable)	10- 15
Follow up duration (if applicable)	Not Applicable
Planned Study Period	12 months
Study End	The study will end when the 10-15 participants data has been collected and analysed and the formal report has been written up. This is anticipated to in September 2025.

Research Question/Aim(s)	Patients Experience and Acceptability of Using a Virtual Reality Headset as an adjunct to rehabilitation following major trauma: An Interview Study
	The aim of this study is to explore the acceptability and usability of an active VR headset intervention as an adjunct to rehabilitation
FUNDING AND SUPPORT	
FUNDER(S)	No funding

ROLES AND RESPONSIBILITIES OF STUDY MANAGEMENT COMMITEES/GROUPS & INDIVIDUALS

This research is being carried out as part of a Master's in Research (MRes) which is being completed at City, University of London. The steering group member are the supervising the project.

Trial Steering Group	
Chair	[name], St George's University Hospital NHS foundation Trust
	[contact]

1 BACKGROUND

There are approximately 22,000 cases of major Trauma in the UK every year (Fisher, A. *et al.*, 2010) and with the addition of the London major trauma centres it has been estimated there is a 19% increase in the odds of survival following major trauma (Moran *et al.*, 2018). (NHS England, 2018) reported this as an additional 1600 patients being saved between 2012-2017.

Whilst more trauma patients are predicted to survive, research has shown there can be a reduction in quality of life after trauma (Vardon-Bounes *et al.*, 2021; Rosenbloom *et al.*, 2013). In a 5-year prospective follow-up study, the final analysis of 55 patients found 17% of patient did not return to work and 36.4% patients were acknowledged as having a disability (Vardon-Bounes *et al.*, 2021). Additionally, in a systematic review of persistent pain and psychological outcomes following musculoskeletal trauma, 28-93% of people reported lasting pain, within a three month to seven-year period post injury (Rosenbloom *et al.*, 2013). This demonstrates a need to find treatments that could help improve pain and recovery in this population.

Promoting early mobilisation and rehabilitation following traumatic injury is recommended, with benefits including maintenance of strength, range of movement, promotion of bowel movements, prevention of deep vein thrombosis, prevention of pressure sores and improved cardio-respiratory function (Guideline NG211, 2022; You, Leighton and Schneider, 2020). However, it should be acknowledged that achieving these recommendations whilst experiencing acute pain can be challenging in this patient group. In a cohort study looking at pain intensity post-surgery, Trauma and orthopaedic patients were amongst those reporting the most significant acute post-surgical pain intensity whilst moving compared with other surgical patients, who had under gone procedure such as major abdominal surgery (Gerbershagen *et al.*, 2013).

Given early mobilisation is recommended in this population, strategies that encourage mobilisation whilst positively influencing patients pain experience might be a useful approach.

A Virtual reality (VR) headset is relatively new technology being explored in many aspects of healthcare, including anatomical and physiology education, patient rehabilitation, public health training, medical training (e.g. surgical skills), viewing medical imagery and children's health (Helou *et al.*, 2023). Software applications have been specifically developed for use in healthcare for the purposes of physical and mental rehabilitation, however further research is required to understand its usefulness and usability particularly in the acute inpatient setting, where research is sparse (Helou *et al.*, 2023). VR headsets are advantageous

compared to other VR devices that have been explored in an inpatient setting as they are more portable and can be wirelessly linked to personal computers (PCs), smartphones, or tablets (Helou *et al.*, 2023).

Currently, a VR headset is being used as an adjunct to inpatients rehabilitation at a London Major Trauma Centre (Fisher, S., Tebbutt and Kenny, 2024). There are very few studies looking at the effectiveness of VR headsets following Major Trauma, and none conducted in the UK health system. One within-person randomised crossover trial, conducted on 60 patients in a single centre in the United States, showed VR to be safe and found it to have a modest tangible effect on pain (Morris *et al.*, 2023). An American case study using a single major trauma inpatient, compared doing range of movement exercises versus standard range of movement exercises using no adjuncts (Hoffman *et al.*, 2009). They randomly allocated the order in which the patient was exposed to the intervention and found the VR decreased pain, time spent thinking about pain and increased range of movement (Hoffman *et al.*, 2009). Whilst these studies are promising for the benefits of VR in major trauma patients, they have small sample sizes and are not specific to an NHS major trauma health population.

While evidence of effectiveness is limited, evidence of patients' experience and perceived acceptability of VR headsets is absent, with no qualitative studies examining these outcomes in relation to VR headsets in major trauma patients. This lack of evidence undermines efforts to develop rehabilitation strategies using this technology. Healthcare interventions perceived as being more acceptable by recipients (e.g. patients) and deliverers (e.g. healthcare professionals) are associated positive outcomes including greater uptake and adherence, improved effectiveness and cost-effectiveness and facilitation of implementation, sustainability and scalability (Sekhon, Cartwright and Francis, 2017; Perski and Short, 2021; Proctor *et al.*, 2011). In recognition of these benefits, the latest revision of the MRC's framework for complex interventions recommends assessing acceptability at multiple stages of development and evaluation(Skivington *et al.*, 2021).

The aim of this study is to interview patient who have used a VR headset as adjunct to their major trauma rehabilitation to gain an understanding of their experience and whether they deem it an acceptable treatment adjunct.

2 RATIONALE

According to the National institute of clinical excellence guidelines, rehabilitation should start as soon as possible following traumatic injury (Guideline NG211, 2022). However, many trauma patients face barriers to engaging in rehabilitation including, anxiety, depression, post-traumatic stress disorder, pain, pain catastrophising and fear of movement (Gabbe *et al.*, 2012; Archer *et al.*, 2012). Ways to address these barriers and promote early engagement in rehabilitation, could not only help the patients but also expedite

hospital discharge with ensuing cost savings. Using VR headsets in this population has the potential to support these clinical goals. However, given the physical and psychological complexities that major trauma patients can experience, it is important to gain an understanding of patients' perspectives about whether they think VR is an acceptable tool as part of their rehabilitation.

VR-based exercise therapy has been shown to improve pain and functional ability in different health conditions, such as chronic lower back pain, internal medicine, oncology, fibromyalgia, musculoskeletal shoulder conditions and knee osteoarthritis (Asadzadeh *et al.*, 2021). However, currently there is minimal research on the use of VR headsets specifically to support rehabilitation in the any acute inpatient hospital setting (Mosadeghi *et al.*, 2016; Kolbe *et al.*, 2021). Most inpatient VR headset interventions focus on relaxation therapy which does not necessarily promote early movement (Patterson *et al.*, 2010; Austin and Siddall, 2021; He *et al.*, 2022). As VR technology is becoming more sophisticated and accessible to health services more companies are approaching the NHS to invest in VR headsets for patients. Therefore, the NHS needs to assess the potential costs and benefits to patients and services and explore implementation challenges in different patient populations and settings (Helou *et al.*, 2023).

In our previous early scoping work at St George's hospital, a VR headset (Sync VR Fit) intervention was piloted with major trauma patients as an adjunct to their rehabilitation (N=18) (Fisher, S., Tebbutt and Kenny, 2024). This work reported that 72% found it 'extremely motivating' and 83% would 'definitely recommend' VR use as an adjunct to rehabilitation. However, this feedback was from a small sample of patients, relied on unvalidated questionnaires and was only able to provide only a limited assessment of patients' views.

The updated MRC Framework for developing and evaluating complex interventions (Skivington *et al.*, 2021) recommends assessing the acceptability of the intervention in the feasibility phase (and continually throughout the development and evaluation process) to inform refinement of the intervention and guide the decision to progress. For this purpose, phenomenological qualitative studies are required.

To address this evidence gap relating to patient experience and acceptability, the current study will conduct theoretically informed semi-structure interviews with major trauma patients to explore their experience of using VRHs and assess acceptability.

3 THEORETICAL FRAMEWORKS

This qualitative study will utilise a Phenomenological methodology with thematic analysis. A phenomenological study considers the lived experiences of a phenomenon for several individuals (Creswell and Poth, 2016). Qualitive research attempts to uncover a deeper human experience through open

questioning to produce rich descriptive data (Renjith *et al.*, 2021). Renjith et al. (2021) highlights the benefits this data can have for designing interventions and rationalising there use in healthcare. This approach seems particularly appropriate for this patient population who are often experiencing complex psychological emotions and physical challenges following their injuries (Gabbe *et al.*, 2012).

Thematic analysis is systematic way of offering insight into a data set by identifying patterns or themes, it aims to make sense of a collection of shared experiences (Braun and Clarke, 2012). Braun and Clarke (2012) offer a six-stage approach to analysing a data set which will be used in this qualitative study, this includes:

- 1. Familiarisation- Becoming acquainted with the data set
- 2. Generating initial codes- a label for a feature of data that is potentially relevant to the research question
- 3. Searching for themes- codes transition to themes based on patterned response
- 4. Reviewing potential themes- developing themes are reviewed in relation he coded data and whole data set, themes may be brough together or broader themes divided into more specific themes
- 5. Defining and naming the theme- Clearly state the specifics about each thing and what makes them unique
- 6. Producing the report- provide a compelling narrative about your data based on your analysis

To investigate patient's experience, the study will utilise an inductive and exploratory approach to generate novel insights from patients who have used VR to establish how they feel it might have helped them. An inductive, exploratory approaches seek to investigate areas of research that have been minimally examined it allows for a systematic approach that is flexible enough to accommodate changes in the research focus due to unexpected findings (Rendle *et al.*, 2019).

4 RESEARCH AIM AND OBJECTIVES

Aims: To explore patients' experience and acceptability of using a physically active VR Headset intervention as an adjunct to their rehabilitation following major trauma via semi-structure interview.

5 STUDY DESIGN and METHODS of DATA COLLECTION AND DATA ANALYIS

Study design

Single centre cross-sectional interview study.

Data collection

Data will be collected by using a semi-structured topic guide. Questions relating to the acceptability of the VR headsets are informed by the Theoretical Framework of Acceptability (TFA)(Sekhon, Cartwright and Francis, 2017).

Recruited patients will be contacted over the phone by the Principal investigator to arrange an interview which will be conducted over video call, via Microsoft teams in a private location or face-to-face in a private room when patients attend hospital for follow-up appointments. We will aim to conduct interviews within 1-month of consenting to participate in the study. Face-to-face Interviews will be recorded via a password protected voice recorder and uploaded securely onto a password protected digital site file on a trust computer. For interview conducted by Microsoft teams, the interview will be audio recorded via Microsoft teams and downloaded securely to password protected site file. They will be transcribed by the chief investigator who will remove any identifiable details. The transcribed material will be held on password protected site file on a St George's Trust computer and the audio recording will be deleted immediately after this transcription process.

Data Analysis

Interview transcripts will be analysed using the Thematic Analysis approach described by Braun and Clarke (2006). Interviews will be transcribed with the support of Microsoft transcription software. Transcriptions will be uploaded to NVIVO for data analysis. Here transcriptions will be coded, codes will be developed into themes, themes will be reviewed and further synthesised once all the data has been captured. Following this the themes will be clearly defined which will guide the production of the final report (Braun and Clarke, 2006).

To investigate the acceptability of VR headsets from the patients' perspective, the TFA will be used (Sekhon, Cartwright and Francis, 2017). This framework posits seven constructs that reflect the underlying key dimensions of acceptability of healthcare intervention (Affective attitude, Burden, intervention coherence, ethicality, opportunity costs, perceived effectiveness and self-efficacy) Sekhon, Cartwright and Francis, 2017)

These constructs inform the interview topic guide (see Appendix 7). To analyse data relating to acceptability a 2-stage process with be completed. In stage 1, text from the interview transcripts will be deductively coded into the seven TFA constructs to provide the core corpus of data for analysis. In stage 2, text within each construct will be inductively analysed to construct themes that reflect the content and meaning of the data.

Rigour

In TA, Braun and Clarke (2019) explain the importance of reflexivity in the study design. This requires a researcher to acknowledge their assumptions and positionings and the impact this has on the data analysis (Braun and Clarke, 2023; Braun and Clarke, 2021).

In this instance the researcher is a clinician already utilising VR in a Major Trauma setting therefore they may have pre-conceived notions of its benefits that they will seek out during coding and theme development. By taking a conscious inductive and reflective approach in data analysis the researcher is trying to minimise the risk of this. The researcher will approach the data with an open mind and consider whether there could be alternative explanations for themes identified. To further reduce the risk of bias in this study, the researcher will utilise the support of academics who do not have experience of using VR in a major Trauma setting to review themes generated from the data and challenge conclusions drawn from this.

To ensure rigour of analysis, we will use methods to enhance Lincoln & Guba's (1985) widely applied concepts of credibility, transferability, dependability and confirmability approach. We will reflect on our ability to meet these criteria in the final report (Lincoln, 1985).

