7.3 Recruitment

7.3.1 Participant identification

In the Trauma and Orthopaedic team at St George's we have split clinical and research roles that work across the T&O department as treating therapists and within research. These staff members have training in Good Clinical Practice (GCP) and will appear on the study delegation log. They will be responsible for patient identification and recruitment.

There are two main methods for identifying patients:

- Major trauma Physiotherapists and occupational therapists who are using the Virtual Reality (VR)
 headset with major trauma inpatients will highlight the patients to the research team. The Research
 physiotherapists that work within the Trauma and Orthopaedic team will formally screen the
 patients for eligibility. The chief investigator and delegated research physiotherapists will approach
 the patients on the ward to invite them to participate in the study.
- 2. The Major trauma therapy team is due to start another trust approved quality improvement project in September 2024 on the use of the VR headsets in Major Trauma. The patients who have used the VR headset as part of their inpatient rehabilitation are being asked if they would mind being contacted, after discharge, by the T&O therapy team about future research or quality improvement projects relating to VR in Major Trauma. If they agree to this, it is being documented within their medical notes and being recorded as part of the quality improvement project. Therefore, there will also be a list of potentially eligible patients that could be approached by the research physiotherapists over the phone to invite them to participate. Anyone approached and consented via this method will undergo interview within 12-months or having used the headset, to ensure recent exposure to the device and more accurate reflections on their experience.

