- How was the headset supposed to help your rehabilitation?
- Was there any advantage to using the headset (compared to not using it)?
- Did it make sense to you to wear the headset to help your recovery? [why?]

Perceived effectiveness

Q.8) Do you think using the headsets helped your rehabilitation? [how? why?]

Prompts:

- Did the headsets help you to recover more quickly?
- Did the headsets help you to recover more completely?
- If you had not used the headsets do you think you would have recovered as well as you have?

Opportunity costs

Q.9) Did the time and effort that it takes to use the headset prevent you from doing other activities that are important to you?

Prompts:

- Did using the headsets stop you from resting, reading, talking to family/ friends?
- Did using the headsets stop you from engaging in other important rehabilitation activities?

Ethicality

Q.10) Do you think there are any ethical issues raised by the use of the headsets for patients like you?

Prompts:

- Did somebody explain the reason for using the headsets to you before you were invited to use them?
- Did you feel that you could have refused to use the headsets if you had wanted to? [Did you feel
 pressured into using them?]
- Did you have any concerns about safety risks or side-effects of using the headsets?
- Did the headset make you feel vulnerable?
- Do you think the headsets would be appropriate for all patients? [Would any patients not be able to use them?]
- Are you concerned about the headsets collecting personal data about you?
- Did you feel embarrassed wearing the headset? [are they childish?]

Q.11) Overall, would you that using the headsets was an acceptable part of the rehabilitation process or not? [Prompt for elaboration / explanation]

That's all my questions for you, but before we finish:

Q.12.) Is there anything else that you would like to tell me about your experience of using the headsets?

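### The protocol lets clinicians who may have treated a participant take consent and interview, and its bias safeguards start only at coding, so acceptability answers are at risk of leaning favourable

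*Protocol*

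**What the plan says.** **Who recruits and takes consent.** Protocol section 7.3.1 gives identification and recruitment to staff with "split clinical and research roles that work across the T&O department as treating therapists and within research". The chief investigator also approaches patients on the ward. Under section 7.3.2, consent may be taken on the ward, at a later outpatient appointment or by phone.

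**Who interviews.** Section 5 says: "Recruited patients will be contacted over the phone by the Principal investigator to arrange an interview". Section 6 refers only to the researcher conducting the interview. Section 8.1 names the lead researcher, an experienced physiotherapist, as the person able to recognise severe distress.

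**What bias is recognised.** The Rigour part of section 5 states: "In this instance the researcher is a clinician already utilising VR in a Major Trauma setting". It adds that "they may have pre-conceived notions of its benefits that they will seek out during coding and theme development".

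**What is done about it.** There are four measures:
- "By taking a conscious inductive and reflective approach in data analysis the researcher is trying to minimise the risk of this".
- The researcher considers alternative explanations for themes.
- Academics without experience of VR in this setting "review themes generated from the data and challenge conclusions drawn from this".
- The closing commitment to trustworthiness criteria begins "To ensure rigour of analysis, we will use methods to enhance".

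**What is asked.** Appendix 7 covers liking (Q4), perceived benefit (Q8), ethicality (Q10) and overall acceptability (Q11). One prompt under Q10 is: "Did you feel that you could have refused to use the headsets if you had wanted to".

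**The concern.** Acceptability to patients is the aim of the study (section 4), and section 2 says such evidence informs refinement of the intervention and the decision to progress. If the person asking delivered or offered the headset, a patient may soften criticism out of courtesy or because care is continuing. That bias would arise while the data are being generated, and its expected direction is towards acceptability. It would matter most for the questions on refusal and pressure, where an honest negative answer criticises the conduct of staff and not the device.

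The team's earlier pilot (section 2, N=18) was already strongly favourable: 72% found VR extremely motivating and 83% would definitely recommend it. A further favourable result adds most if readers can see that courtesy to the treating clinician was guarded against.

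**Working it through.** No formula applies and the plan gives no figure to reproduce. The check sets the sections side by side.

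1. **Can the roles overlap?** Section 5 says the researcher uses VR clinically in major trauma. Section 7.3.1 says the recruiting staff are also treating therapists. The contacts table describes the chief investigator as a Trauma and Orthopaedics physiotherapist. Overlap is possible.

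2. **Does anything exclude it?** Sections 5 (Data collection), 6, 7.3.1, 7.3.2 and 8.1 contain no rule against consenting or interviewing one's own patient. The case report form in Appendix 6 has no item for a treating relationship.

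3. **Where does each safeguard act?**
   - Inductive, reflective stance: placed in data analysis.
   - Alternative explanations: applied to themes already identified.
   - Outside academics: themes and conclusions.
   - Trustworthiness criteria: introduced as rigour of analysis.

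   All four act on words already spoken. They can correct how the researcher reads an answer, but not an answer that was never given.

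4. **Does the protocol recognise that who is in the room matters?** Yes, in section 8.4. The patient group warned that in focus groups people might hold back their views of the intervention, and favoured one-to-one interviews. The same question is not asked about the interviewer.

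5. **Which questions are exposed?** Q4 to Q11 are the acceptability questions: 11 - 4 + 1 = 8. Q4, Q8, Q10 and Q11 ask for a judgement on care the interviewer may have given, which is 4 of 8. Q1 also has the interviewer speak of the trauma unit as 'our' unit, which identifies the speaker with the treating team.

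6. **How many interviews?** The documents give no share of participants treated by the consent-taker or interviewer. The number could be anywhere from none to all of the 10-15, and nothing in the plan narrows it.

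**The case against.** The strongest reply is that the overlap is inferred. Under the first route in section 7.3.1, the therapists using the headset refer patients to a research team, which then screens and approaches them. That is some separation, and working across the department does not show that a research physiotherapist delivered VR to a given participant.

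The interview stage is also not unprotected:
- Patients have at least 24 hours to consider taking part.
- Interviews are by video or at follow-up appointments, so mostly after discharge.
- Section 8.1 requires a reminder that withdrawing does not affect care.
- The guide asks about dislikes, discomfort, pressure, safety worries and embarrassment.
- The Rigour section discloses the researcher's position, and reflexive work asks for positioning to be acknowledged, not removed.

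Much of this stands, and it limits the claim. It does not close the gap. The reminder concerns withdrawal, not critical answers, and is listed as distress mitigation. The scripted opening in Appendix 7 omits it and does not say that criticism is welcome. Negative prompts help, but do not settle who asks them. Disclosure covers the analysis and does not reach recruitment or interviewing.

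Three stronger readings are tempting, and the documents support none of them:
- That the interviewer did treat participants. No section says so.
- That answers will lean favourable, or that a favourable finding could not be told apart from politeness. Direction is an expectation and size is unknown, and prompted interviews can still yield specific criticism.
- That a number of affected interviews can be estimated. Any assumed share would have no basis in the protocol.

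The participant information sheet and consent form were not available here, so what participants are told about staff roles cannot be judged.

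**Conclusion.** The point holds as a risk. The protocol permits a clinician who uses VR, and research staff who also treat, to consent and interview patients they may have treated. Every measure it names against bias applies at coding, theme review or later. Four of the eight acceptability questions are exposed to a risk of favourable answers.

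The absence of a rule can be read directly from the text. The direction of bias rests on the ordinary assumption that patients are reluctant to criticise their own clinicians to their face. The number of participants affected and the size of the bias cannot be derived. This is a low-cost improvement on the study's main question, best made before the first interview. It does not invalidate the design.

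**What to change.** 1. **Sections 7.3.1 and 7.3.2:** have consent taken by a delegated research physiotherapist who did not deliver rehabilitation or VR to that participant.
2. **Section 5, Data collection:** have interviews done, where feasible, by a delegated team member who did not treat the participant. Reconcile this with section 8.1, which limits access to identifiable audio to the lead researcher.
3. **Appendix 6:** add an item recording whether the consent-taker or the interviewer treated the participant. Report it, and consider it when interpreting themes.
4. **Section 5, Rigour:** extend reflexivity to recruitment and interviewing.
5. **Appendix 7, opening and Q1:** state the interviewer's role truthfully, say that critical views are wanted and that answers will not affect care, and replace 'our' with 'the' before trauma unit.

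Do not promise that treating staff will not learn individual answers unless section 8.8 is amended. It gives the Trauma and Orthopaedic research associates the full dataset, and section 7.3.1 describes research staff who also treat.

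**Cost.** Consent can be reallocated among the GCP-trained staff already planned. Interviewing needs more: section 7.3.1 delegates only identification and recruitment, so the delegation log must be extended and any second interviewer prepared. Expect some scheduling effort, and the student may not conduct every interview. A substitute from the same department may still attract deference to the unit, so the change reduces the risk without removing it. Where separation proves impossible, the recorded relationship still lets readers judge.
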